## **STATEMENT OF COMPLIANCE FOR NON-DRUG OR DEVICE CLINICAL TRIALS**

This document is a protocol for a clinical research study. The study will be conducted in compliance with all stipulations of this protocol, the conditions of ethics committee approval, the [NHMRC National Statement on Ethical Conduct in Human Research](#) (as updated) and the [Handbook for Good Clinical Research Practice \(GCP\). The Therapeutic Goods Act has adopted ICH Guideline for Good Clinical Practice.](#)

## Contents

### 1. GENERAL INFORMATION

#### 1.1 Protocol title and date

Swallowing Therapy in People with Parkinson’s Disease using Principles of Motor Learning and Ultrasound Biofeedback, August 2024

#### 1.3 Name of the study funders

No external funding

#### 1.6 Trial registration - Trial identifier and registry name

The Australian New Zealand Clinical Trials Registry (ANZCTR), (reg number to be provided once registered)

### 2. SYNOPSIS

TITLE	Effect of Swallowing Therapy on Efficiency of Eating and Drinking in People with Parkinson’s Disease using Principles of Motor Learning and Ultrasound Biofeedback
CLINICAL PHASE	I/II
STUDY TYPE:	Behavioural intervention
PRIMARY HYPOTHESES	Participants will show an improvement in swallowing outcomes with the use of rehabilitation combining principles of motor learning and ultrasound biofeedback. No improvement in control outcomes will be observed.
DESIGN	Part 1 - Single Case Experimental Design to determine feasibility of treatment paradigm in a single participant with PD followed by Part 2 - a multiple baseline within participants Single Case Experimental design to determine treatment efficacy.
BLINDING/MASKING	This is a pilot, behavioural intervention trial. Therefore, treating clinicians and participants cannot be blinded to intervention.

	Clinicians assessing outcome measures will be blinded to the sequence in which the probe data is collected and the stage of the study the participant is in.
OUTCOMES	
The primary outcome measures include:
 
 
• Timed Water Swallow Test (TWST) (Hughes & Wiles, 1996; Sarve et al., 2021)
 
• Test of Masticating and Swallowing Solids (TOMASS) (Athukorala et al., 2014; Huckabee et al., 2018)
 
 
Secondary outcome measures:
 
 
• Texture of food as per the International Dysphagia Diet Standardisation Initiative Level (IDDSI) (Cichero et al., 2017)
 
• Consistency of liquid as per the the International Dysphagia Diet Standardisation Initiative Level (IDDSI) (Cichero et al., 2017)
 
• Observational measures rated with an ultrasound probe under the chin. 
 
○ Changes in components 2, 3, 4 and 5 listed on the Modified Barium Swallow Impairment Profile (MBSImP) (Martin-Harris et al., 2008) which is a rating scale that rates key physiological aspects of swallowing in the different phases. Components 2, 3, 4, and 5 are specifically related to the oral phase of swallowing.
 
○ Average time taken to swallow a single sip of liquid (ml/s)
 
○ Time taken to swallow (a) ½ biscuit (b) a dessert spoon of diced fruit and (c) a dessert spoon of puree
 
○ Number of times the participant needs to swallow to clear a single, controlled sip of liquid (number of swallows/ml)
 
○ Number of times the participant needs to swallow to clear (a) ½ biscuit (b) a dessert spoon of diced fruit and (c) a dessert spoon of puree from their mouth
 
 
 
• Patient reported measures: 
 
○ Time taken to complete meals
 
○ Swallowing Quality of Life Questionnaire (SWAL-QoL) (McHorney et al., 2002)
 
○ Theoretical Framework of Acceptability based questionnaire (Sekhon, Cartwright & Francis, 2022)
 
 
 
 
Control measures
 
 
• Maximum Phonation Time (Speyer et al., 2010)
 
• Speech Rate (Syllables per minute during a 30 second monologue)
 
• Average decibels in 30 second monologue
 
• Intelligibility Rating of monologue using the Frenchay-2 Rating scale (perceptual) (Enderby & Palmer, 2008)
 

STUDY DURATION	Estimated study duration from initial enrolment until completion of data analyses is 24 months.
INTERVENTION/S	Behavioural dysphagia rehabilitation with ultrasound biofeedback

NUMBER OF PARTICIPANTS	n=6 based on requirement of at least 3 participants to carry out a single case experimental design as part of a pilot study and to account for attrition.
POPULATION	
Sample Size: n=6
 
Gender: Male and Female
 
Age: Adults > 50 years old
 
Demographic group: Those diagnosed with Idiopathic Parkinson’s Disease
 
General Health Status: To be eligible for this study, participants will have to be living in the community
 
Geographic Location: Assessment and treatment will be conducted at The University of Sydney or at participants’ place of residence within Sydney metropolitan area

SELECTION AND ENROLMENT	
Inclusion Criteria: Participants with:
 
 
1. Confirmed diagnosis of Idiopathic Parkinson’s Disease by a neurologist
 
2. Self-reported change in swallow function in the last 12 months
 
3. Ability to assent to participation in study (either verbal or written)
 
4. Presence of oral phase dysphagia as assessed by a speech pathologist.
 
5. Medically stable and living in the community.
 
 
Exclusion Criteria: Participants who are/have:
 
 
1. Other concomitant neurological disorders
 
2. A history of head and neck cancer
 
3. Unmanaged hearing or vision difficulties (self-report)
 
4. Nil by Mouth status.
 
5. Unable to communicate in English
 
6. Hospitalised with a respiratory tract infection in the last 12 weeks.
 

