## Probes

As shown on page 8, Probes for Phase A1 and A2: The TWST and TOMASS and a measurement of maximum phonation time and a 30 second monologue will be obtained 6 times for those allocated in the 2-week baseline periods and 9 times for those allocated in the 3-week baseline period.

Probes for Phase B: Treatment probes will be taken twice weekly (on the day of the first and last therapy session each week) for 4 weeks. Treatment probes will be identical to the baseline probes and will be collected immediately before therapy commences on that day.

The probes will take approximately 30-40 minutes and breaks will be provided if a participant experiences fatigue.

After the end of Phase B, a repeat assessment will be completed (identical to the one conducted at the start of the treatment program) by a qualified speech pathologist. Participants will also be asked to complete a Theoretical Framework of Acceptability Questionnaire to understand their acceptance and the feasibility of the intervention.

As this is a pilot, the frequency and duration of the treatment sessions, the duration and frequency of breaks provided, the type of foods and fluids used, the amount and type of feedback provided and the number of times the participant is asked to swallow and sets of swallows may be altered based on participants' fatigue level and response to the therapy protocol.

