### **6.5 Primary and Secondary Outcome Measures**

The primary outcome measures include:

- Timed Water Swallow Test (TWST) (Hughes & Wiles, 1996; Sarve et al., 2021)

- Test of Masticating and Swallowing Solids (TOMASS) (Athukorala et al., 2014; Huckabee et al., 2018)

Secondary outcome measures:

- Texture of food as per the International Dysphagia Diet Standardisation Initiative Level (IDDSI) (Cichero et al., 2017)
- Consistency of liquid as per the the International Dysphagia Diet Standardisation Initiative Level (IDDSI) (Cichero et al., 2017)
- Observational measures rated with an ultrasound probe under the chin.
  - Changes in components 2, 3, 4 and 5 listed on the Modified Barium Swallow Impairment Profile (MBSImp) (Martin-Harris et al., 2008) which is a rating scale that rates key physiological aspects of swallowing in the different phases. Components 2, 3, 4, and 5 are specifically related to the oral phase of swallowing.
  - Average time taken to swallow a single sip of liquid (ml/s)
  - Time taken to swallow (a) ½ biscuit (b) a dessert spoon of diced fruit and (c) a dessert spoon of puree
  - Number of times the participant needs to swallow to clear a single, controlled sip of liquid (number of swallows/ml)
  - Number of times the participant needs to swallow to clear (a) ½ biscuit (b) a dessert spoon of diced fruit and (c) a dessert spoon of puree from their mouth
- Patient reported measures:
  - Time taken to complete meals
  - Swallowing Quality of Life Questionnaire (SWAL-QoL) (McHorney et al., 2002)
  - Theoretical Framework of Acceptability based questionnaire (Sekhon, Cartwright & Francis, 2022)
  - Swallowing Disturbance Questionnaire - PD (SDQ-PD)

Control measures

- Maximum Phonation Time (Speyer et al., 2010)
- Speech Rate (Syllables per minute during a 30 second monologue)
- Average decibels in 30 second monologue
- Intelligibility Rating of monologue using the Frenchay-2 Rating scale (perceptual) (Enderby & Palmer, 2008)

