### **6.14 Statistical analyses**

As per standard procedure for single case within participant studies, experimental and control measures will first be graphed and visually inspected for change. If the visual inspection indicates change over time, statistical analysis will be completed. As multiple, repeated measures will be taken for each participant, the data will first be analysed for correlations. If the correlation coefficient was not significant, the assumption of independence in measurements will be made, and effect sizes within participant will be calculated using  $d_2$  as this measure is appropriate for single case data (Beeson & Robey, 2006).

In the presence of serial dependency between data points, the data will be analysed using percent of nonoverlapping data (PND) (Scruggs, Mastropieri & Casto, 1987). PND is a commonly used calculation to measure change in measures taken across research phases. The highest data point in the baseline (A1) phase is compared across all research phases. The number of data points either above or below that value is calculated as a percentage of the total number of data points. The higher the number of nonoverlapping data points, the stronger the effect.

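### Half of the primary hypothesis says the control measures will not improve, but the plan supports it only by not seeing change and never compares swallowing change with control change

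*Protocol*

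**What the plan says.** The primary hypotheses in the protocol synopsis have two parts. The first is "Participants will show an improvement in swallowing outcomes with the use of rehabilitation combining principles of motor learning and ultrasound biofeedback"; the second is "No improvement in control outcomes will be observed". Section 6.5 lists four control measures: maximum phonation time, and speech rate, average decibels and rated intelligibility, the last three all taken from the 30-second monologue.

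Section 6.14 sets out how the series are judged: "experimental and control measures will first be graphed and visually inspected for change". It continues: "If the visual inspection indicates change over time, statistical analysis will be completed". If the measurements are taken as independent, "effect sizes within participant will be calculated using" d2. If they are serially dependent, the percentage of nonoverlapping data (PND) is used, read as "The higher the number of nonoverlapping data points, the stronger the effect". Both statistics describe one series at a time.

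Under Probes, the measures are taken in each of phases A1 and A2 "6 times for those allocated in the 2-week baseline periods and 9 times for those allocated in the 3-week baseline period". Phase B adds two probes a week for four weeks, which makes eight.

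**The concern.** The first part of the hypothesis claims an effect and the second claims the absence of one. Not seeing change in 6 or 9 noisy probes is weak evidence of absence. The gate in section 6.14 adds to this: a control series that looks flat gets no d2 or PND, so its change is not even quantified.

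The controls carry much of the inference. Participants and the therapist are unblinded. Randomised baseline lengths guard against time trends, and assessors blind to recording order guard against rating bias. Neither guards against a real but non-specific gain, from effort, alertness or attention, that begins when therapy begins. Only comparison with the controls addresses that, and two separate verdicts are not a comparison. One series can cross the threshold and the other miss it although both changed by the same amount.

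**Working it through.** **No figure to reproduce.** The protocol gives no alpha, SD, effect size or definition of visible change, and n=6 is not derived from a formula. What follows is an illustration under stated assumptions.

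**Inputs.** From the protocol: n = 6 or 9 probes in each of A1 and A2, 8 probes in phase B, four controls, six participants with a minimum of three. Assumed: independent normal probes with SD 1, the same true gain g (in SD units) in one swallowing and one control series, the two series independent, and a one-sided 5% t-test of A2 against A1 in place of the visual verdict.

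**Chance that one series is judged improved.** The statistic is noncentral t with 2n-2 degrees of freedom and noncentrality g√(n/2). Call the resulting probability p. The misleading pattern (swallowing improved, control not) has probability p(1-p).

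| g | n | p | p(1-p) |
|---|---|---|---|
| 0.5 | 6 | 0.201 | 16% |
| 0.5 | 9 | 0.265 | 19% |
| 1 | 6 | 0.488 | 25% |
| 1 | 9 | 0.650 | 23% |
| 2 | 6 | 0.942 | 5.5% |
| 2 | 9 | 0.992 | 0.8% |

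Simulation agrees (25% and 23% at 1 SD, 5.6% and 0.9% at 2 SD). A lag-1 correlation of 0.3 leaves the 1-SD figures at 25% and 23%.

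**Other verdict rules.** With 6 baseline and 8 treatment probes and a 1-SD gain, five stand-in rules (a t-test, standardised change of at least 0.8 or 1, PND of at least 50% or 70%) give 14% to 25%. If the control has the same raw gain but twice the probe SD, the range is 16% to 45%. If the two series correlate at 0.5, it is 12% to 19%.

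**All four controls must be flat.** With independent, equally sensitive controls the pattern has probability p(1-p)^4. At 1 SD this is 0.488 × 0.512^4 = 3.4% (6 v 6) and 0.650 × 0.350^4 = 1.0% (9 v 9). With 6 and 8 probes it is 3% to 5% over three of the verdict rules. Correlation among the controls raises it: for 6 v 6, about 10% at correlation 0.5 and 16% at 0.8.

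**Replication.** If the pattern had to appear in each of three independent participants, 0.25^3 = 1.6%.

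**Does a direct contrast cure it?** It depends on how it is built (equal gains, no specificity):

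- Swallowing minus control at each session, SD known, independent probes: 5% one-sided, as intended. With lag-1 correlation 0.3 it is about 11%.
- The same after dividing each measure by the participant's own A1 SD, with a plain t-interval: 8% at 1 SD, 14% at 2 SD and 20% at 3 SD (6 v 6), against a nominal 5%. The estimated SDs turn equal gains into unequal ones.
- The difference in standardised change averaged over participants, with a t-interval from the spread between participants: about 2.5% or slightly less per side of a 95% interval, with three or six participants.

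**The case against.** The strongest reply has four parts.

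- **The protocol predicts; it does not conclude.** It never writes that a specific effect will be declared, section 4.2 has no control hypothesis, and section 6.3 describes a study to acquire data for a sample size calculation. This stands in part. A reader might infer that the protocol runs an equivalence test or has a formal specificity rule, and it has neither. But the paired statement is labelled a primary hypothesis, the measures are labelled controls, and Part 2 is said to determine efficacy.
- **The 25% is selective.** This stands. A reader might infer that a quarter of participants, or the trial as a whole, would falsely show specificity. The figure is per participant, for one control, near the worst gain size. Four controls and replication reduce it, though three controls share one monologue and are unlikely to be independent.
- **The opposite failure.** A reader might also infer that one drifting control among 4 × 6 = 24 series refutes the hypothesis; with no true change and a 5% false-positive rate in independent series, none would flag with probability 0.95^24 = 29%. The protocol states no such rule. It cannot be combined with the single-control 25%, because the two assume different rules.
- **The analysis plan may add a margin or contrast.** It may, and their absence from the protocol is not the point. The point is what the protocol does fix: the no-effect wording, and a gate that leaves a flat-looking control unquantified.

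**Conclusion.** The point holds as a matter of inference: the plan supports its no-improvement claim for the controls by absence of visible change and does not compare the two changes. An equal non-specific gain can therefore be read as swallowing only. The risk is material for modest gains, roughly 0.5 to 1.5 SD, and larger if a control is noisier than the swallowing tests. It is small for large gains, which would usually show in both series. All rates rest on assumed normal, mostly independent probes and on stand-ins for a visual rule that the protocol does not define. It should be changed, because the remedy is cheap and this half of the hypothesis cannot otherwise be supported.

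**What to change.** 1. Reword the second part of the hypothesis: improvement in swallowing outcomes will exceed change in control outcomes.
2. In section 6.14, compute the standardised change for every swallowing and control series, signed so that positive means improvement, whatever the visual verdict.
3. Name one control in advance as the comparator, for example maximum phonation time, and report the other three as supportive.
4. Report the swallowing-minus-control difference in standardised change, averaged over participants, with an interval from the between-participant spread. Give it per participant only with an interval that allows for estimation of the SD and for serial correlation, not a plain t-interval on values divided by the A1 SD.
5. Report control change with its interval, and do not state that controls did not improve from absence of visible change alone.

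**Cost.** No new data: swallowing and control measures are taken at the same probes. The changes are to wording and analysis, though a valid per-participant interval takes some care. Precision is the price. Under the simple known-SD contrast, power for a specific 2-SD effect is about 74% (6 v 6) or 88% (9 v 9), against 94% or 99% for a single measure. The averaged interval has half-width t/√n times the between-participant SD: 2.57/√6 = 1.05 with six participants and 4.30/√3 = 2.48 with three. Some specificity claims will be weaker. An ordinal control with no baseline variation, possible for the intelligibility rating, cannot be the comparator.

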### 3. RATIONALE / BACKGROUND

Up to 82% of people with Parkinson’s Disease (PD) experience dysphagia (swallowing difficulties) (Kalf et al., 2012). The presence of dysphagia in people with Parkinson’s Disease (PwPD) is associated with poorer quality of life (Leow, Huckabee, Anderson & Beckert, 2010), increased burden of care (Perry, Borders, Dakin, & Troche, 2022), and increased risk of malnutrition, dehydration, and chest infections (Carrión et al., 2019).

One of the key features of Parkinson’s Disease is bradykinesia where movements are slower and smaller than desired, impacting multiple body functions like speaking, walking, eating and drinking (Beradelli, Rothwell, Thompson & Hallett, 2001). With eating and drinking, the slower and more inefficient movements make it difficult for PwPD to safely and efficiently move food, liquid and saliva in their mouth (oral phase) and throat (pharyngeal phase) (Suttrup & Warnecke, 2016). While there are effective swallowing rehabilitation

options for the pharyngeal phase of swallowing, there is limited research evidence on rehabilitating the oral phase in PwPD (Gandhi, & Steele, 2022).

In other body functions such as speech and walking, drawing attention to the overall movement and providing external or augmented feedback during rehabilitation was effective in combatting bradykinesia and improving speech intelligibility and gait respectively (Schulz et al., 2021; Muthukrishnan, Abbas, Shill & Krishnamurthi, 2019). Therefore, incorporating external or augmented feedback which allows PwPD to be aware of the movement of their tongue while swallowing will be helpful in rehabilitating the oral phase in PwPD.

Ultrasound is a low-cost, portable and non-invasive tool that allows a person to see the way their tongue is moving in real time while eating or drinking (Potente et al., 2023). Ultrasound has been used in other patient groups as a visual biofeedback tool to rehabilitate the oral phase of swallowing (Hsiao, Wu & Wang, 2021). For example, amongst tongue cancer survivors the use of ultrasound tongue visual biofeedback during the oral phase of swallowing resulted in increased efficiency in swallowing food and liquids (Blyth, McCabe, Madill, & Ballard, 2017). In this approach, an ultrasound probe was placed under the chin and a real time video image of the tongue within the mouth was seen by the speech pathologist and patient while the patient was eating or drinking (Blyth, McCabe, Madill, & Ballard, 2017).

Given the usefulness of external feedback in rehabilitation for PwPD, integrating the use of ultrasound biofeedback technique as per Blyth and colleagues is likely to enhance swallowing rehabilitation of the oral phase in PwPD. Ultrasound visual biofeedback will be provided in a structured swallow rehabilitation program. The rehabilitation program will incorporate principles of motor learning such as systematically practising swallowing food and liquid multiple times instead of practising isolated tongue movements as use of these improves the overall effectiveness of swallow therapy (e.g., Zimmerman, Carnaby, Lazarus, & Malandraki, 2020).

## **4. AIMS & HYPOTHESES**

### **4.1 Aims:**

- 1) To develop and determine the feasibility of a training program which targets movement of food / liquid in the mouth with the use of ultrasound visual feedback and principles of motor learning to rehabilitate oral phase swallowing disorders amongst PwPD.
- 2) To determine the effectiveness of the developed training program on improving the efficiency of swallowing and QOL in PwPD.

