### **4.2 Hypotheses:**

People with Parkinson's Disease with dysphagia who participate in a four-week intervention using ultrasound visual feedback and principles of motor learning will show improvements in their swallowing efficiency (i.e., reduction in time taken to swallow liquid and food)

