#### Schedule for individual participants from recruitment to follow-up:

**Tasks and Data Collected during Assessment and Probes:**

TIMING	Screener	Assessment	Phase: A1 Baseline Pre-treatment Baseline Probes	Phase: B Treatment Probes	Phase: A2 Baseline post-treatment		Phase C: Four week follow up
					Post-treatment Assessment	Maintenance Probes	
TASKS		1-2 visits	three times weekly across baseline period	1st and 3rd therapy session each week,	same day as the 1st maintenance probe	three times weekly across the baseline period	once, 4 weeks after the last therapy session
Screening (Questionnaire of demographic Information and inclusion/exclusion criteria)	X						
Timed Water Swallow Test (Hughes & Wiles, 1996; Sarve et al., 2021) (Video Recording)		X	X	X	X	X	X
Test of Mastication and Swallowing Solids (Athukorala et al., 2014; Huckabee et al., 2018) (Video Recording)		X	X	X	X	X	X
Information regarding time taken to complete meal and IDDSI Level (Cichero et al., 2017) (Images of food, Questionnaire)		X	X	X	X	X	X
Clinical Swallow Evaluation with Ultrasound using the MBSImp Rating Scale (Martin-Harris et al., 2008) for oral phase components (Video recording)		X	X	X	X	X	X

Swallowing Quality of Life Questionnaire (SWAL-QoL) (Questionnaire) (McHorney et al., 2002)		X				X		X
Theoretical Framework of Acceptability Questionnaire (Sekhon, Cartwright & Francis, 2022) (Questionnaire)						X		
Maximum Phonation Time (MPT) (Speyer et al., 2010) (Audio Recording)		X	X	X	X	X	X	X
Swallowing Disturbance Questionnaire (SDQ-PD) (Manor et al., 2007) (Questionnaire)	X					X		X
30 second monologue (Audio Recording)		X	X	X	X	X	X	X
North Wind and the Sun passage (Amundsen & Hansen, 2014) (Audio Recording)		X				X		X
Picture description (Audio Recording)		X				X		X
Rate at which participants can accurately repeat a series of rapid, alternating sounds as per published normative data (Kent, Kim & Chen, 2022) (Video Recording)		X	X	X	X	X	X	X

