## Assessment

Following screening and consent, participants will be assessed by a qualified speech pathologist (one of the investigators) using standard speech pathology tools. As shown on page 8, the assessment will include the (a) Timed Water Swallow Test (TWST) (Hughes & Wiles, 1996; Sarve et al., 2021), (b) Test of Masticating and Swallowing Solids (TOMASS) (Athukorala et al., 2014; Huckabee et al., 2018), (c) a clinical swallow trial with the ultrasound to determine severity of oral phase deficits based on a checklist based on components 2, 3, 4 and 5 of the Modified Barium Swallow Impairment Profile (MBSImp) (Martin-Harris et al., 2008) (d) questions about the type of modification they need for the meal based on the The International Dysphagia Diet Standardisation Initiative Level (IDDSI) (Cichero et al., 2017), (e) the time taken to complete meals, and the (f) Swallowing Quality of Life Questionnaire (SWAL-QoL) (McHorney et al., 2002).

Control measures including the (a) Maximum Phonation Time, (b) Speech Rate (Syllables per minute during a 30 second monologue), (c) Average decibel in 30 second monologue and (d) Percent Intelligibility Rating based on Frenchay-2 Rating scale (perceptual) (Enderby & Palmer, 2008) will be recorded.

The assessment will be audio and video recorded. If participants experience fatigue, the assessments will be conducted over 2 sessions.

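### Aim 2 claims effectiveness on quality of life, but the SWAL-QoL is never given in the baseline or treatment phase, so any change in it is an uncontrolled before-after difference

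*Protocol*

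**What the plan says.** Section 4.1 states the second aim as determining how effective the training program is in "improving the efficiency of swallowing and QOL in PwPD". QOL stands level with efficiency and is not marked as exploratory. The hypothesis in section 4.2 is narrower. It predicts shorter swallowing times and does not mention QOL. Section 6.5 lists the SWAL-QoL among the secondary, patient-reported outcomes.

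Section 6.1 describes a single-case experimental design with multiple baselines. There is no parallel group, and participants are randomised only to the length of the baseline phase.

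In the schedule for individual participants (section 6.2), the row that begins "Swallowing Quality of Life Questionnaire (SWAL-QoL) (Questionnaire" carries three marks: initial assessment, post-treatment assessment and four-week follow-up. The Assessment section confirms the first. The Probes section leaves the questionnaire out of the repeated probes: "The TWST and TOMASS and a measurement of maximum phonation time and a 30 second monologue will be obtained 6 times" under the two-week baseline, and 9 times under the three-week baseline. It adds that treatment probes have the same content as baseline probes, and that the assessment is repeated after phase B.

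Section 6.14 justifies its methods with the clause "As multiple, repeated measures will be taken for each participant". It then sets out visual inspection, a check for serial correlation, and either d2 or the percentage of nonoverlapping data (PND) against the A1 phase.

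**The concern.** In a single-case design, the inference comes from seeing a measure stay level through an untreated phase and then shift when treatment begins, at different times in different participants. A measure that is not taken in the untreated phase gets none of that protection. The SWAL-QoL has one score before treatment and none in A1 or B, so it cannot show whether the score was already moving, or how much it varies from one occasion to the next.

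At stake is what the trial may conclude. If aim 2 stands as written, a before-after change in self-report from between three and six people could be reported as effectiveness on QOL. That change would mix any treatment effect with retest variation, the passage of time, expectation, the attention of many visits, and disease course. Section 7.2.1 itself warns that function may decline through progression, so the distortion could go either way. A later analysis plan cannot repair this, because a pre-treatment score that was not collected cannot be recovered once therapy has begun.

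**Working it through.** **Inputs.** Baseline probes three times weekly for 2 or 3 weeks (schedule table; Probes). Treatment probes twice weekly for 4 weeks (Probes). SWAL-QoL at the initial assessment, post-treatment assessment and follow-up (schedule table; Assessment; Probes). Planned n = 6 (synopsis; section 6.3); minimum data set n = 3 (section 6.7.3).

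**Step 1: reproduce the plan's own counts.** A1 probes: 3 × 2 = 6 and 3 × 3 = 9, which match the 6 and 9 in the Probes section. Phase B probes: 2 × 4 = 8.

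**Step 2: count the observations per participant.**

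| Measure | Initial assessment | A1 | B |
|---|---|---|---|
| TWST, TOMASS | 1 | 6 or 9 | 8 |
| SWAL-QoL | 1 | 0 | 0 |

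After treatment the SWAL-QoL is given twice more, at the post-treatment assessment and at follow-up: 1 + 0 + 0 + 1 + 1 = 3 in all. The columns of the schedule table are not perfectly aligned in its later rows, but the three marks agree with the Assessment and Probes sections.

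**Step 3: ask which of the trial's safeguards reach QOL.**

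- *Staggered baselines.* They work by comparing scores on either side of the A1/B boundary. QOL is not measured in either phase, so the stagger gives it no control.
- *Blinding (section 6.4.3).* Recordings are re-ordered so that assessors do not know the phase. The SWAL-QoL is completed by the participant, who knows the phase.
- *Control measures (section 6.5).* All four are voice or speech tasks: phonation time, speech rate, loudness and intelligibility. None would reveal an expectation or attention effect on a questionnaire.

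**Step 4: ask what one pre-treatment score can provide.** A standard deviation from m scores has m − 1 degrees of freedom. With m = 1 that is 0, so the spread is undefined, and neither a trend nor a serial correlation can be estimated.

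**Step 5: an illustration of what is lost.** This is not the error rate of any planned analysis. Assume no true change, exchangeable scores and no ties. The chance that both later scores are better than all m earlier ones is 1 / C(m + 2, 2):

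- m = 1 (the present schedule): 1/3 = 33.3%
- m = 2 (one added A1 score): 1/6 = 16.7%
- m = 6: 1/28 = 3.6%
- m = 9: 1/55 = 1.8%

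A single early score says little about one participant. One added score helps, but falls well short of the replication that the primary tests have.

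**The case against.** The best reply is that nothing confirmatory rests on QOL. The hypothesis covers efficiency only, the primary outcomes are the TWST and TOMASS, and the study describes itself as a pilot that gathers data for a later sample size calculation. Probing the primary targets often, and giving a longer questionnaire before, after and at follow-up, is a normal choice for a secondary outcome. All of this stands, and it is why the weight is moderate. It does not remove the mismatch, because aim 2 still claims effectiveness on QOL.

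Several stronger readings are tempting, but the documents do not support them:

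- *That section 6.14 breaks down for the SWAL-QoL.* Its opening words could be read to cover every measure, but it never expressly assigns d2 or PND to the questionnaires. A descriptive analysis may be set out elsewhere.
- *That scores will regress from an extreme value at enrolment.* The eligibility criteria ask for a self-reported change in swallowing and for oral phase dysphagia. They set no SWAL-QoL threshold, so nobody is selected on that score. Some regression through correlated self-report is possible, but its existence and size are not shown.
- *That the only pre-treatment score is taken exactly 2 or 3 weeks before therapy.* The protocol gives the length of the baseline, not the gap between the assessment and the first probe.
- *That the chance of every participant improving is a false-positive rate for this trial.* No such decision rule is planned. The weakness is lack of control, not a computed error rate.

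**Conclusion.** The point holds at moderate weight. The design can address effectiveness on swallowing efficiency, which is measured repeatedly in A1 and B. It cannot address effectiveness on QOL, which has 1 score before treatment, 0 in A1 and 0 in B. Describing how each participant's SWAL-QoL moved from before treatment to after it and to follow-up remains legitimate. Attributing that movement to the therapy does not.

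The conclusion rests on the schedule as written and on the SWAL-QoL being the only quality-of-life instrument named. Meal duration and diet level are collected at the probes according to the schedule table, but they are not quality-of-life measures and do not fill the gap. The conclusion needs no assumption about effect size, variance or regression to the mean. A reader should not infer that the efficiency half of aim 2 is affected.

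As a side note, the SDQ-PD also has a single pre-treatment value, from the screener. It measures swallowing disturbance and is not named in aim 2, so it adds nothing to the argument.

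**What to change.** 1. Reword aim 2 so that effectiveness refers to swallowing efficiency only, and state that SWAL-QoL change will be reported descriptively for each participant. This alone removes the contradiction and brings the aim into line with the hypothesis.
2. Also give the SWAL-QoL at the last A1 probe visit and use that score as the pre-treatment reference. The change from the initial assessment to the last A1 visit then shows each participant's movement without treatment, beside the movement from the last A1 visit to post-treatment.

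The cost is one further questionnaire at a visit that already takes place, a few minutes of participant burden, and a more modest QOL claim. The second change does not make QOL a full single-case outcome. Two scores give a no-treatment comparison, but not a baseline trend or a usable estimate of variability, so the rewording is needed even if the extra score is collected.
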